3.8 Coding dictionaries

Medical history and ADRs will be coded using version 16.1 of the Medical Dictionary for Regulatory Activities (MedDRA®). For coding of prior and concomitant medication, version Sep 2013 of World Health Organization Drug Dictionary (WHO DD) will be used.

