4.8 Examination of subgroups

The primary endpoints will be summarized by the following subgroups, if at least 25 patients fall into that subgroup:

- Starting dose of LCM (high starting dose - first dose ≥ 200 mg/day; titration – first dose < 200 mg/day)
- Prior tumor treatment (radiotherapy; chemotherapy; surgery; radiotherapy and chemotherapy; radiotherapy and surgery; chemotherapy and surgery; radiotherapy, chemotherapy and surgery)
- Concomitant tumor treatment (radiotherapy; chemotherapy; surgery; radiotherapy and chemotherapy; radiotherapy and surgery; chemotherapy and surgery; radiotherapy, chemotherapy and surgery)
- Number of different types of lifetime AEDs (1; 2; 3; 4)
- Core AED therapy (including but not limited to levitiracetam, valproate sodium, lamotrigine, oxcarbazepine, zonisamide, topiramate, pregabalin, gabapentin, phenytoin, carbamazepine, clonazepam, clobazepam, phenobarbital, valproic acid, ergenyl chrono; combinations of these therapies)

Note: Each subject can be only in 1 category for "Core AED therapy"

- Age (≥ 16 - ≤ 18 ; > 18 - < 65 ; ≥ 65)
- Sex (male; female)
- Historical seizure frequency (1; 2-5; 6+)
- Historical seizure type (Partial-onset seizures with secondary generalization; Partial-onset seizures without secondary generalization; Both)
- Time since tumor diagnosis (≤ 1 month; > 1 - ≤ 3 months; > 3 - ≤ 6 months; > 6 months - ≤ 12 months; > 12 - ≤ 24 months; > 24 months)
- Type of brain tumor (astrocytoma; oligodendrolioma; mixed [oligo-astro]; ependymoma; other)
- WHO grade (1; 2; 3; 4)
- Karnofsky performance status (<60%; 60%; 70%; 80%; 90%; 100%)

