6.4 Prior and concomitant medications

The number and percentage of patients who used prior and concomitant medications (including chemotherapy and AEDs) will be summarized according to the anatomical therapeutic class main group, the therapeutic subgroup, and the generic drug name.

Prior medications are those medications started before the first dose of study drug. Medication taken after the first dose of study medication will be regarded as concomitant medication whether the start date is before, after or on the date of the first dose of study medication. Lifetime AEDs are AEDs with an end date before the first dose of study drug.

The core AED will be summarized separately using the “Core AED?” question on the CRF to select the relevant medications. The core AEDs are the AEDs that the patient is receiving at Baseline.

The number and percentage of patients according to Core AED therapies will be summarized according to preferred term combination.

The number and percentage of patients who had prior or concomitant radiotherapy will be summarized. The total dose in gray (Gy) and number of fractions will be summarized as continuous variables.

Rules for defining concomitant medications with missing dates are provided in [4.2.2](#).

All prior and concomitant medication and radiotherapy will be listed.

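### The core AED subgroup lists valproate sodium and valproic acid as separate therapies with no rule to pool them, so one Baseline regimen can be split below the 25-patient floor

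*SAP*

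**What the plan says.** SAP 4.8 makes core AED therapy one of the subgroup variables for the primary endpoints. The list opens with levetiracetam and goes on: "valproate sodium, lamotrigine, oxcarbazepine, zonisamide, topiramate, pregabalin, gabapentin, phenytoin, carbamazepine, clonazepam, clobazepam, phenobarbital, valproic acid, ergenyl chrono; combinations of these therapies". It is introduced as non-exhaustive. A note adds: "Each subject can be only in 1 category for" core AED therapy. Results are summarised "if at least 25 patients fall into that subgroup".

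SAP 8.1.2.1 and 8.1.2.2 apply these subgroups to the responder rate (with a Clopper-Pearson 95% CI) and to PGIC.

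SAP 6.4 handles the same variable in the medication tables: "The number and percentage of patients according to Core AED therapies will be summarized according to preferred term combination". For prior and concomitant medication in general, AEDs included, it tabulates by ATC main group, "the therapeutic subgroup, and the generic drug name". On coding, SAP 3.8 says only that "version Sep 2013 of World Health Organization Drug Dictionary (WHO DD) will be used". None of these sections says whether salt, acid and brand entries of one active substance are pooled.

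**The concern.** Valproate sodium is, by its name, the sodium salt of valproic acid. A subgroup by Baseline AED is meant to show how lacosamide performs when added to a given drug, and the form in which that drug was coded is not the question. Three features of SAP 4.8 act together: two entries for one drug, mutually exclusive categories, and a minimum size. Patients on the same regimen can be divided so that neither part is large enough to show, although together they would be. A regimen of valproate plus a given second AED can be divided in the same way. At stake is whether a planned subgroup row appears for responder rate and PGIC, and whether the core AED table shows one regimen on one line or two.

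**Working it through.** **Inputs**
- Minimum subgroup size: 25 (SAP 4.8).
- Evaluable patients: 93 of 100 enrolled (SAP 2.4).
- Expected responder rate: 0.60, with a CI half-width of 0.10 (SAP 2.4).
- Baseline AEDs per patient: 1 or 2 (Protocol 8.1, criterion 10).
- Valproate use: not given in either document. All user counts below are assumptions.

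**The plan's own figure.** N = (1.96/0.10)² x 0.60 x 0.40 = 92.2, rounded up to 93. The stated sample size reproduces and is not in dispute.

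**When the split hides a result.** Let T be the number of patients who would share one category if the two terms were pooled, for example valproate as the only Baseline AED. Pooled, the category is shown when T ≥ 25, which is 25/93 = 26.9% of evaluable patients. Under two labels nothing is shown when the larger label holds at most 24. Both conditions can hold from T = 25 up to T = 2 x 24 = 48 (48/93 = 51.6%). At T = 49 one label must hold at least 25.

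How uneven the split can be while still hiding the result (larger label ≤ 24):

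| T | Most uneven split still hidden | Share under larger label |
|---|---|---|
| 25 | 24/1 | 96% |
| 30 | 24/6 | 80% |
| 40 | 24/16 | 60% |
| 48 | 24/24 | 50% |

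Close to the floor almost any split hides the row. Towards 48 only a near-even one does.

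**What would be lost.** Take T = 30 with 18 responders (60%). Pooled, the row would read 60% with a Clopper-Pearson 95% CI of 40.6% to 77.3%. Split 15/15, no row appears.

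**Limit set by combinations.** SAP 4.8 lists combinations alongside the single drugs and, read with SAP 6.4, each combination is its own category. T therefore counts patients within one category, not all valproate users. If 30 patients take valproate and 10 of them take a second AED, the pooled valproate-alone group is 30 - 10 = 20. It stays below 25 with or without pooling.

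**The case against.** The strongest reply is that the list is illustrative, that dictionary coding may already bring the two terms together, and that the analyses are descriptive. On the first, the list is the only specification of the categories, and a programmer following it would create both. On the second, how the dictionary version groups salts cannot be seen from the documents. SAP 6.4 also uses generic drug name for medications in general but preferred-term combination for core AEDs. The third point stands and limits the weight of the finding: no objective concerns the type of Baseline AED, and no primary estimate changes.

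A reader might infer more than the documents support:
- **That a third label raises the ceiling to 3 x 24 = 72.** This needs Ergenyl Chrono to be a valproate product. The documents do not say what it contains.
- **That a switch between forms counts as two lifetime AEDs.** SAP 6.4 defines lifetime AEDs as those that ended before the first lacosamide dose. A form still taken at Baseline is a core AED, so only the stopped form counts. Two would arise only if both forms had ended and were counted as different types, a term that SAP 4.8 leaves undefined.
- **That the site's spelling drives the split.** Medications are coded, and the core AED table uses preferred terms rather than verbatim text.
- **That valproate use is lost from the tables.** The general table is by generic name, all medications are listed, and exclusive core AED rows can be added by hand.

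**Conclusion.** The point holds as a defect in the stated categorisation. Following SAP 4.8 as written separates patients on the same Baseline regimen, and 25 to 48 patients in one true category could yield no subgroup result for either primary variable. Two things are assumed: that the two preferred terms remain distinct after coding, and that enough patients share one regimen. Neither can be checked from the documents. If few patients take valproate, if nearly all are coded under one term, or if most take it in varied combinations, the split changes little or nothing. The effect is confined to which descriptive subgroup rows appear and how the core AED table reads. The primary estimate and its interval are untouched. This is a free improvement, not an error that threatens the study's conclusions.

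**What to change.** Before database lock, define core AED therapy in SAP 4.8 and 6.4 by active substance, and add a short table mapping each preferred term to its substance. Pool valproate sodium and valproic acid as valproate. Map Ergenyl Chrono to its active substance once the coded data confirm it. Form combinations only after mapping, so that a patient recorded under both valproate terms is not taken for a two-drug combination. Use the same mapping when counting different types of lifetime AEDs. The cost is one small table and a line of text in each section. No new data are needed and no planned method changes.

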5 STUDY POPULATION CHARACTERISTICS

5.1 Subject disposition

The number and percentage of patients in each population (ES, SS, FAS and modified FAS) will be presented. The number of patients in each population will also be provided by investigator in addition to the dates of first patient in and the last patient out for each center.

Study eligibility criteria, patients who did not meet any of these criteria as well as patient disposition, patient analysis sets and visit dates will be provided in listings.

The number and percentage of patients who started treatment with LCM, completed, and discontinued from the study will be presented for the SS together with a summary of primary reason for prematurely terminating the study. Subjects who discontinued the study prematurely will be listed.

5.2 Protocol deviations

The number and percentage of patients with at least 1 important protocol deviation in each of the categories defined in the Important Protocol Deviations Template will be summarized for the SS and modified FAS. Percentages for single deviations are based on the number of patients with any deviation.

All important protocol deviations for patients in the ES will be listed by site, patient number, and protocol deviation category.

6 DEMOGRAPHICS AND OTHER BASELINE CHARACTERISTICS

If not stated otherwise, the following analyses will be performed for the SS, the FAS and the modified FAS. Corresponding listings will be based on the ES.

6.1 Demographics

The following demographics will be summarized and listed:

- Age (years) – continuous and categorized as (≤ 18 , $> 18- < 65$, ≥ 65 years)
- Gender (male, female)

6.2 Other Baseline characteristics

The following characteristics will be summarized at Baseline:

- Time since tumor diagnosis (years) – continuous
- Type of brain tumor (astrocytoma, oligodendrolioma, mixed [oligo-astro], ependymoma, other)
- Tumor (WHO) grade (1, 2, 3, 4)
- Karnofsky performance status

Details of concomitant procedures and procedure history will be listed. Karnofsky performance status and tumor characteristics will also be listed at Baseline and post-Baseline assessments.

6.3 Medical history and concomitant diseases

Medical history will be summarized for the SS by MedDRA system organ class (SOC) and preferred term (PT), displaying the number and percentage of patients with history present overall as well as for each SOC and each PT. Medical history and a glossary for medical history will be listed.

6.4 Prior and concomitant medications

The number and percentage of patients who used prior and concomitant medications (including chemotherapy and AEDs) will be summarized according to the anatomical therapeutic class main group, the therapeutic subgroup, and the generic drug name.

Prior medications are those medications started before the first dose of study drug. Medication taken after the first dose of study medication will be regarded as concomitant medication whether the start date is before, after or on the date of the first dose of study medication. Lifetime AEDs are AEDs with an end date before the first dose of study drug.

The core AED will be summarized separately using the “Core AED?” question on the CRF to select the relevant medications. The core AEDs are the AEDs that the patient is receiving at Baseline.

The number and percentage of patients according to Core AED therapies will be summarized according to preferred term combination.

The number and percentage of patients who had prior or concomitant radiotherapy will be summarized. The total dose in gray (Gy) and number of fractions will be summarized as continuous variables.

Rules for defining concomitant medications with missing dates are provided in [4.2.2](#).

All prior and concomitant medication and radiotherapy will be listed.

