8 SELECTION AND WITHDRAWAL OF PATIENTS

8.1 Selection criteria

Before any data are collected for any patient in this NIS, written data consent will be properly executed and documented.

The following selection criteria must be followed for patients entering the NIS:

1. Patient has never been treated with LCM prior to this NIS or treatment with LCM for the first time started no earlier than 7 days prior to enrollment in this NIS.
2. The decision by the treating physician to prescribe LCM falls within current standard clinical practice, and the treatment decision is clearly separated from the decision to consider inclusion of the patient in the NIS.
3. A Patient Data Consent form is signed and dated by the patient and/or by the parent(s) or legal representative.
4. Patient is a male or female ≥ 16 years of age.

5. Patient must have a diagnosis of BTRE secondary to low-grade glioma (World Health Organization Grade 1 to 2 at time of enrollment).
6. Patient has a retrospective Baseline seizure frequency of at least 1 partial-onset seizure in the 8 weeks prior to start of LCM treatment.
7. Patient does not have a previous diagnosis of epilepsy before tumor onset.
8. Patient does not have brain metastases.
9. Patient has a Karnofsky performance status scale index $\geq 60\%$.
10. Patient is currently taking only 1 or 2 Baseline AEDs for epilepsy other than LCM.
11. Patient has received a maximum of 4 different lifetime AEDs ever before entering the NIS.

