3.3 Definition of Baseline values

Concomitant AEDs at Baseline are defined as AEDs given at the start date of LCM or the date of Visit 1 in case of a missing start date of LCM.

For all other variables, Baseline data are the values collected at Visit 1.

Baseline for the partial-onset seizure frequency per 28 days will be derived from the data of the Historical Seizure Count form as described in Section 3.10.4.

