3.10.3 Time since first diagnosis

The time since first diagnosis will be given in years and will be derived applying all the rules for missing date imputation (see Section 4.2.3) with the following formula:

$$(\text{Start date of LCM} - \text{date of diagnosis}) / 365.25$$

Only completed years will be considered, ie, decimal places will be ignored. In cases where the start date of LCM is missing, the date of Visit 1 will be used instead.

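### The lifetime-AED subgroup in SAP 4.8 has no level for eligible patients who score 0 under the SAP 6.4 definition

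*SAP*

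**What the plan says.** **Lifetime AEDs.** SAP 6.4 gives the definition: "Lifetime AEDs are AEDs with an end date before the first dose of study drug". The same section keeps ongoing drugs apart: "The core AEDs are the AEDs that the patient is receiving at Baseline". SAP 3.3 fixes the date: "Concomitant AEDs at Baseline are defined as AEDs given at the start date of LCM". SAP 4.8 then lists the subgroup factor as "Number of different types of lifetime AEDs (1; 2; 3; 4", and the list ends there.

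**Eligibility.** Protocol 8.1 has two relevant criteria. Criterion 10: "Patient is currently taking only 1 or 2 Baseline AEDs for epilepsy other than LCM". Criterion 11: "Patient has received a maximum of 4 different lifetime AEDs ever before entering the NIS". Criterion 11 sets a maximum and no minimum, and does not say whether Baseline AEDs count towards it. No criterion asks for an AED that has been stopped.

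**Time since diagnosis.** SAP 3.10.3 divides the days from diagnosis to LCM start by 365.25 and adds: "Only completed years will be considered, ie, decimal places will be ignored". It does not say which diagnosis. SAP 4.8 uses bands in months, starting "Time since tumor diagnosis (≤ 1 month; > 1 - ≤ 3 months" and continuing to more than 24 months, six bands in all. SAP 6.2 lists time since tumour diagnosis as a continuous variable in years.

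**Use.** SAP 8.1.2.1 and 8.1.2.2 present the responder rate (with a Clopper-Pearson interval) and the PGIC in each 4.8 subgroup. SAP 3.5.3 assigns subgroup analyses to the FAS. Protocol 11.3.3 leaves subgroup detail to the SAP.

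**The concern.** The definition in 6.4 and the levels in 4.8 appear to count different things: the definition counts stopped AEDs, while levels running from 1 to 4 suit AEDs ever taken. A programmer who follows 6.4 has nowhere to put a patient who adds LCM to a first AED, or to two first AEDs that are both ongoing. A programmer who follows the levels produces a different table under the same title.

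At stake is a planned subgroup display of both primary variables. Some eligible patients would drop out of it without notice, and the remaining row labels would not mean what a reader takes them to mean.

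The time-since-diagnosis bands raise a smaller question of the same kind. The only derivation the SAP gives for time since a diagnosis yields whole years, which is coarser than most of the bands.

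**Working it through.** **1. The plan's own size, for context.** With p = 0.60 and half-width 0.10, n = 1.96² × 0.60 × 0.40 / 0.10² = 92.2, rounded up to 93. At n = 93 the half-width is 1.96 × √(0.24/93) = 0.0996. The stated 93 evaluable patients reproduce. The point does not depend on this figure; it serves only to size the subgroups in step 5.

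**2. Possible lifetime-AED scores.** Let E be the distinct AEDs ever taken, other than LCM, and C those ongoing (1 or 2, criterion 10). With complete dates, and no ongoing AED that also had an earlier ended course, the 6.4 score is E − C. If criterion 11 includes Baseline AEDs, E is at most 4:

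| E | C | 6.4 score (E − C) | Row in 4.8 under 6.4 | Row if all AEDs were counted |
|---|---|---|---|---|
| 1 | 1 | 0 | none | 1 |
| 2 | 1 | 1 | 1 | 2 |
| 2 | 2 | 0 | none | 2 |
| 3 | 1 | 2 | 2 | 3 |
| 3 | 2 | 1 | 1 | 3 |
| 4 | 1 | 3 | 3 | 4 |
| 4 | 2 | 2 | 2 | 4 |

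Two of the seven pairs score 0 and have no row. Row 1 holds patients with E of 2 or 3, and row 4 is always empty. Counting all AEDs gives 1 to 4, exactly the listed levels. These are counts of pairs, not of patients.

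If criterion 11 excludes Baseline AEDs, the stopped count runs from 0 to 4 and E from 0 + 1 = 1 to 4 + 2 = 6. Score 0 is still possible and still has no row; the listed levels then fit neither count exactly.

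**3. How many patients.** The documents do not say. As an assumption only, a share of 10% to 60% of 93 would be about 9 to 56 patients. A share of 27% (25/93) would be enough for the missing group itself to meet the 25-patient display rule.

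**4. Time since diagnosis, if 3.10.3 applies.** Completed years = floor(days/365.25); one month = 365.25/12 = 30.44 days.

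| Days | Months | Days/365.25 | Completed years | Band in 4.8 (months) |
|---|---|---|---|---|
| 30 | 0.99 | 0.08 | 0 | up to 1 |
| 91 | 2.99 | 0.25 | 0 | over 1 to 3 |
| 182 | 5.98 | 0.50 | 0 | over 3 to 6 |
| 365 | 11.99 | 0.9993 | 0 | over 6 to 12 |
| 366 | 12.02 | 1.002 | 1 | over 12 to 24 |
| 730 | 23.98 | 1.9986 | 1 | over 12 to 24 |
| 731 | 24.02 | 2.001 | 2 | over 24 |

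Four of the six bands share the value 0. The two longest bands are separated correctly.

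**5. How many rows can appear.** With 93 patients, 3 × 25 = 75 fits and 4 × 25 = 100 does not, so at most three mutually exclusive rows per factor can be shown. With 100 patients, four are possible.

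**The case against.** **Impact.** The strongest reply is that little depends on this. All summaries are descriptive, rows appear only with at least 25 patients, and no count of affected patients is available, so the affected rows might never be printed. That stands, and it is why the point is minor. The SAP is also to be read with the annotated CRF, which is not among the documents and may show how lifetime AEDs are recorded. That is a fair limit, but it does not change the definition the SAP gives.

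**The 6.4 definition may be meant only for medication tables.** This does not hold up. In the current SAP text the term appears only in 6.4 and 4.8, and no separate lifetime-AED table is planned.

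**Tempting stronger readings that the documents do not support:**

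- A reader might infer that the 6.4 score is below the number of AEDs ever taken by 1 or 2 for every eligible patient. SAP 4.2.1 treats an AED with no end date as ongoing and moves a missing end day to the end of the month, so a stopped AED can go uncounted and the gap can exceed 2. An ongoing AED with an earlier ended course can narrow it. Criterion 10 applies at entry, while SAP 3.3 looks at LCM start, which can be up to 7 days earlier.
- A reader might infer that the month bands flatly contradict 3.10.3. That section does not name the tumour, its truncation may be meant only for the years variable in 6.2, and its subtraction already gives an analyst what the bands need. What remains is a conditional request for clarification.
- A reader might treat the absence of a no-treatment level under prior and concomitant tumour treatment as a further conflict. It is an incomplete list and contradicts no definition.

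**Conclusion.** The lifetime-AED part holds on the text. Following 6.4 leaves eligible patients without a stopped AED outside a planned subgroup summary of both primary variables, and generally puts patients with two or three AEDs ever taken in row 1. The missing level 0 does not depend on how criterion 11 is read. The exact fit of levels 1 to 4 to AEDs ever taken does: it assumes that the limit of four includes Baseline AEDs.

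The time-since-diagnosis part is secondary. It holds only if 3.10.3 governs the tumour variable and its truncated value is the input to the bands.

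Severity is minor: the consequence is confined to descriptive FAS subgroup tables subject to the 25-patient rule. The overall responder rate, the overall PGIC summary and the sample size do not change.

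**What to change.** **Lifetime AEDs.** State one of the following in SAP 4.8 and 6.4:

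- For this subgroup, count all distinct AEDs other than LCM taken before the first LCM dose, including core AEDs. This is close to the wording of criterion 11 but not identical, since study entry can fall up to 7 days after LCM start.
- Or keep the 6.4 definition, add level 0, and label the rows as stopped AEDs.

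**Time since tumour diagnosis.** State that the 4.8 bands use the untruncated interval from tumour diagnosis to LCM start, in months. The precision of the tumour diagnosis date is not given. If only month and year are collected, as SAP 3.10.4 says for the epilepsy diagnosis, the earliest-date rule in SAP 4.2.3 can overstate the interval by up to 30 days (30/30.44 = 0.99 month). The shortest bands would then stay approximate, and the SAP should say so.

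**Cost.** A few words in SAP 3.10.3, 4.8 and 6.4 and minor table programming. No new type of assessment is needed.
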